## SECTION I: RESEARCH PLAN

1. **Statement of Purpose:** State the scientific aim(s) of the study, or the hypotheses to be tested.

The specific aims of Sub-study #1 are:

Specific Aim #1: DEVELOPMENT: We will update our current Invite Only VR prototype into a polished videogame intervention using input from 4 focus groups of 5 adolescents each (n = 20), aged 12-17 and the extant literature. These focus groups will inform the development of the VR videogame intervention, *Invite Only VR*, for e-cigarette prevention among teens.

Specific Aim #2: EVALUATION: Conduct a pilot randomized controlled trial with 300 teens ages 11-15 comparing the Invite Only VR intervention vs. an attention/control non-health-related VR videogame, collecting assessment data at baseline, post-gameplay, three months and six months to determine:

- a. the preliminary impact of the intervention on knowledge, intentions, perceptions, attitudes, social norms, self-efficacy and behaviors related to: i) initiation of e-cigarette use, ii) e-cigarette use cessation.
- b. the intervention's acceptability and feasibility by collecting quantitative and qualitative data on teens' satisfaction and gameplay experience of the intervention.
- c. preliminary evidence of the impact of *Invite Only VR* on players' perception and experience of social pressure and social norm development.

The specific aim for Sub-study #2 is

Specific Aim #1: EVALUATION: Conduct a quasi-experimental effectiveness trial of the Invite Only VR intervention using a pre-post study design with 400 teens ages 11-15, collecting assessment data at baseline and post-gameplay to determine:

- a. the preliminary impact of the intervention on knowledge, intentions, perceptions, attitudes, social norms, self-efficacy and behaviors related to: i) initiation of e-cigarette use, ii) e-cigarette use cessation.
- b. the intervention's acceptability and feasibility by collecting quantitative on teens' satisfaction and gameplay experience of the intervention.

2. **Probable Duration of Project:** State the expected duration of the project, including all follow-up and data analysis activities.

2 years

3. **Background:** Describe the background information that led to the plan for this project. Provide references to support the expectation of obtaining useful scientific data.

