We will conduct the proposed research for the study in two phases. Phase I consists of: (a) the continued development of our current *Invite Only VR* prototype into a polished videogame intervention using input from 4 focus groups of 5 adolescents each (n = 20), aged 12-17 and the extant literature. These focus groups will inform the development of the VR videogame intervention, *Invite Only VR*, for e-cigarette prevention among teens (Specific Aim #1). In Phase II, we will conduct a randomized controlled trial with 300 teens ages 11-15 comparing the *Invite Only VR* intervention vs. an attention/control non-health-related VR videogame, collecting assessment data at baseline, post-gameplay, three months and six months to determine: 1) the preliminary impact of the intervention on knowledge, intentions, perceptions, attitudes, social norms, self-efficacy and behaviors related to initiation of e-cigarette use and e-cigarette use cessation, 2) the intervention's acceptability and feasibility by collecting quantitative and qualitative data on teens' satisfaction and gameplay experience of the intervention, and 3) preliminary evidence of the impact of *Invite Only VR* on players' perception and experience of social pressure and social norm development.

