**Conduct focus groups to gather data to inform refinement of the current videogame prototype, *Invite Only VR*.**

We will conduct 4 focus groups (5 adolescents each) to collect feedback on the game content, art, narrative, and characters, and gameplay mechanics. We will use visual tools (e.g., storyboards, pictures) to facilitate the discussions. We will conduct the focus groups according to standard dual-facilitator procedures. We anticipate that 4 focus groups will be adequate to achieve thematic saturation. The focus groups will be conducted such that ideas and themes from one discussion inform discussion topics and prompts used in the next focus group. Participants will be compensated with a gift card for \$25. Audio recordings of each session will be transcribed, reviewed and discussed by the research team to refine the videogame intervention. As a part of the game development, with parental permission we will invite selected students to the Yale recording studio on campus to provide voices for the videogame characters.

**Conduct randomized controlled trial:** We will enroll 300 adolescents to test *Invite Only VR* using a pre/post design to evaluate the preliminary efficacy of the videogame prototype, *Invite Only VR*. Participants will be randomly assigned to play either Invite Only VR (n=115), or receive standard care as usual (n=115). Participants will accumulate between 1.5-2 hours of game play over 2 sessions (approximately one week, meeting twice). Participants will play the *Invite Only VR* game on a VR headset for 45 mins to 1 hour, one to two times per week for 2 weeks (to accumulate up to 1.5 - 2 hours of gameplay). This total duration and number of sessions is consistent with those found in effective smoking prevention interventions among adolescents and with the amount of time adolescents play videogames. Participants will have a 10 min break in the middle of each session and will be instructed that they may take additional breaks as needed.

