**Measures.** We will collect data on participant demographics at baseline. At baseline and immediately after gameplay, and again at 3 and 6 months post gameplay, we will collect data on intentions to initiate smoking, self-efficacy for refusing offers of e-cigarettes and other tobacco products, perceived social norms related to smoking, attitudes about smoking, and smoking behavior using validated questionnaires. Finally, we will assess satisfaction with game play and acceptability and feasibility of the intervention by collecting self-report data at the end of the game play period. All assessments will be conducted via face-to-face interviews with a research assistant and each adolescent.

**Study locations.** For the focus groups and pilot-testing, the study will take place at one of the after-school programs with which the play2PREVENT Lab has ongoing partnerships including but not limited to: Wilbur Cross High School (which serves 1300 students from 9th to 12th grade), Hamden Youth Center (which serves roughly 75 adolescents in the 6th through 12th grade, and the Milford Middle School District (which serves 1300 students the majority of whom are between the ages of 11 and 14), and LEAP (which serves over 1000 children between the ages of 7-18). For the randomized controlled trial, we will enroll students from the Milford Middle School District between the ages of 11-15.

**Participants, screening, and consent.** In collaboration with community program staff, we will discuss the study with interested parents and adolescents and collect eligibility screening data. If the participant is eligible and interested we will proceed with the consent procedures that will differ by phase of the research. For focus groups, we will give information sheets to the adolescents and to their parents describing the purpose of and protocol for the focus groups. Parents who do not wish for their children to participate will contact the project director. No forms will be signed for focus groups. For the randomized controlled trial, we will obtain written, informed assent (adolescent) and consent (parent).

In addition to paper forms for parental consent for participation in the randomized controlled study, we will also provide a web-based form for parents to review and electronically sign through Yale Qualtrics.

For Sub-study #2:

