|  Decisionally Impaired |  Employees                         |  Pregnant women and/or fetuses           |
|  Yale Students         |  Females of childbearing potential |                                                                  |

NOTE: Is this research proposal designed to enroll children who are wards of the state as potential subjects?

Yes  No

8. **Inclusion/Exclusion Criteria:** What are the criteria used to determine subject inclusion or exclusion?

For the focus groups and pilot-testing, inclusion/exclusion criteria are: participants must be 12-17 years of age and speak English. For the randomized controlled trial, participants must be between the ages of 11-15, Speak English, and be able to play a mobile app-based videogame and VR videogame (willing to sit with a smartphone or tablet computer and/or use a VR headset for 45-60 minutes/session to play the game). Eligibility will be determined by the research team.

9. How will **eligibility** be determined, and by whom?

Eligibility will be determined by the research team. If a prospective participant meets the inclusion criteria, they will be eligible to participate in the project.

10. **Risks:** Describe the reasonably foreseeable risks, including risks to subject privacy, discomforts, or inconveniences associated with subjects participating in the research.

The potential risks associated with this study have to do with maintenance of the confidentiality of the identities of the participants enrolled in the study and information relating to them. De-identified hard copies of the data will be stored in locked cabinets and electronic data will be stored in secure, password-protected computers. Only the P.I. and other relevant research staff will have access to the data.

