Statistical procedures and models for analyzing data have been selected according to the research hypotheses being investigated and the types of data available. In general, we will use two-tailed tests and p-values smaller than 0.05 will be considered to indicate statistical significance. When necessary, however, we will use appropriate adjustment of the level of significance (alpha) to account for multiple statistical tests. All statistical analyses will be conducted on an intention-to-treat sample using either SPSS/SAS statistical packages. Baseline characteristics will be analyzed using descriptive statistics.

We will evaluate the efficacy of Invite Only VR at reducing initiation of e-cigarette use (primary outcome). We will test the hypothesis that individuals who play Invite Only VR will be less likely to report the initiation of e-cigarette use in comparison to the control condition. We will conduct a longitudinal analysis using a linear mixed models approach to compare participants in the intervention group to participants in the control group on e-cigarette use from baseline across all follow-up assessments. An advantage of mixed models is that participants with missing data need not be excluded as all available data are used in estimating parameters. We will also use logistic regression models to determine if any relevant baseline variables are associated with rates of initiation of e-cigarette use (constructed as a binary outcome (Yes/No). We plan to evaluate the prognostic significance of a small set of predictor variables (e.g., knowledge, intentions, perceptions, attitudes, social norms, and self efficacy) and use them as covariates in the primary analysis.

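### The Sub-study #1 randomised trial has two different comparators: a non-health VR game in the aims, undefined standard care in the assignment sentence

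*Combined protocol and SAP*

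**What the plan says.** Section I, item 1 (Statement of Purpose), Specific Aim #2 describes a randomised trial "comparing the Invite Only VR intervention vs. an attention/control non-health-related VR videogame". The Phase II paragraph of item 4 (Research Plan) repeats this: "vs. an attention/control non-health-related VR videogame".

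The paragraph of item 4 on conducting the randomised trial contains the only assignment sentence: "Participants will be randomly assigned to play either Invite Only VR (n=115), or receive standard care as usual (n=115".

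Item 13 (Statistical Considerations) does not name the comparator. Its hypothesis is that players will be "less likely to report the initiation of e-cigarette use in comparison to the control condition", and its analysis will "compare participants in the intervention group to participants in the control group on e-cigarette use".

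Two other places bear on the question:

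- Item 8 (Inclusion/Exclusion Criteria) requires trial participants to "be able to play a mobile app-based videogame and VR videogame", and to be "willing to sit with a smartphone or tablet computer and/or use a VR headset for 45-60 minutes/session to play the game". Neither game nor device is tied to an arm.
- The Sub-study #1 Measures paragraph of item 4 times follow-up as "again at 3 and 6 months post gameplay".

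**The concern.** The comparator defines what a randomised trial estimates. A VR game without health content, played on the same schedule, gives controls the headset, the novelty, the time out of routine and the contact with staff. What remains between the arms is the e-cigarette content. Standard care with no game leaves all of these on the intervention side, so the contrast is the whole package against nothing comparable.

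Both are legitimate trials, but staff working from the assignment sentence and staff working from the aims would run different ones, and no analysis can restore an attention control that was not delivered. The primary outcome is self-reported initiation of e-cigarette use, which may respond to attention and expectation as well as to content. How far staff contact reaches the report itself is also unclear. The Measures paragraph has every assessment done as a face-to-face interview, while Section IV, Confidentiality & Security of Data, item 2 has participants enter the more sensitive data themselves.

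**Working it through.** **1. The text side by side**

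| Place | What controls receive |
|---|---|
| Item 1, Specific Aim #2 | VR game, no health content, as attention control |
| Item 4, Phase II paragraph | The same |
| Item 4, randomised-trial paragraph | Standard care, undefined |
| Item 13 | A control condition or group, unnamed |

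This is current text in one protocol, not an amendment log or a redaction. Sub-study #2 does not explain it, because all its participants play Invite Only VR.

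**2. Whether other passages settle it**

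- The sentence after the assignment sentence gives participants 1.5 to 2 hours of play without naming an arm, which leans towards a control game. The sentence after that names only Invite Only VR.
- Follow-up timed from gameplay also leans towards a control game, since a no-game arm has no such date.
- The eligibility wording covers a mobile game and a VR game, but eligibility applies before allocation and says nothing about arms.

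These lean one way but do not say what the control arm receives.

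**3. Difference in exposure**

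The randomised-trial paragraph gives 45 to 60 minutes per session and a total of 1.5 to 2 hours.

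- 1 session: 0.75 to 1.0 h, below the total
- 2 sessions: 2 × 0.75 = 1.5 h to 2 × 1.0 = 2.0 h, fits
- 3 sessions: 2.25 to 3.0 h, above the total

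So the total corresponds to 2 sessions, which the paragraph also states in its first schedule sentence. The between-arm gap in headset time is 0 with a control game on a matched schedule (the aims do not state the control schedule). With no control game it is 2 sessions, or 1.5 to 2 hours per pupil.

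**4. What that gap could do to the primary comparison (illustration only)**

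The documents give no initiation rate and no estimate of an attention effect, so every rate here is an assumption. Suppose the e-cigarette content has no effect, and attention alone lowers reported initiation by a quarter or a half relative to standard care. The table gives the probability of p<0.05 from exact enumeration of the pooled two-proportion z-test (two-sided 0.05, one time point, no clustering, covariates or dropout). This is simpler than the planned mixed model. Two arm sizes are shown because the assignment sentence gives 115 per arm, while enrolment of 300 split equally gives 300/2 = 150. That mismatch is a separate matter.

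| Assumed standard-care rate | Lowered by | 115 per arm | 150 per arm |
|---|---|---|---|
| 5% | a quarter, to 3.75% | 6.6% | 7.9% |
| 5% | a half, to 2.5% | 14.9% | 19.5% |
| 10% | a quarter, to 7.5% | 10.7% | 11.6% |
| 10% | a half, to 5% | 31.2% | 37.0% |
| 15% | a quarter, to 11.25% | 13.2% | 15.9% |
| 15% | a half, to 7.5% | 44.2% | 54.6% |

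With no shift the probability is 4.7% to 5.2%. The excess is not type I error for the package against standard care, because attention is part of that package. It is the chance of a significant result that would be wrongly credited to content.

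**The case against.** The strongest reply is that the assignment sentence contains a drafting remnant. The aim and the Phase II design agree with each other, the unqualified gameplay sentence and the follow-up timing fit a control game, and one clause would cure the conflict. This is plausible, and it may be what the investigators intend. It does not remove the conflict: the outlying wording sits in the one sentence that tells staff what to allocate.

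The second reply is that the harm is conditional. It needs the assignment sentence to govern and standard care to mean no game. Even then, item 13 claims only less reported initiation than under the control condition, the aims call the evidence preliminary, and usual care is a valid comparator for that hypothesis. This is right as far as it goes. Aims 2a and 2c could still be estimated against standard care, and Aim 2b, on acceptability and feasibility, needs no comparator. What is lost is the attention-controlled comparison that Aim 2 states.

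The third reply is that the illustration rests entirely on assumed rates. That is also correct, and the conclusion does not depend on it. Finally, interviews and self-entry of sensitive items can coexist if pupils enter those answers during the interview. The question of data entry is therefore secondary and does not carry the point.

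**Conclusion.** The concern holds. The protocol gives two incompatible comparators for its randomised trial and describes neither. As written, the primary contrast is undefined.

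The size that follows from the documents is the exposure gap: none with a control game on a matched schedule, against 2 sessions or 1.5 to 2 hours of headset time per pupil if standard care means no game. Both the matched schedule and the absence of a game are assumptions, because the protocol states neither. The effect on the estimated difference in initiation cannot be derived. This should be corrected before the trial is run or reported, because it decides which trial is delivered and what a difference between arms can be said to show.

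**What to change.** State one comparator and use it in Specific Aim #2, the Phase II paragraph, the assignment sentence, the eligibility criteria and Statistical Considerations.

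**Route A, if the aims govern.** Amend the assignment sentence so that controls play a non-health VR game on the same session schedule as the intervention arm. Name and describe that game. First reconcile the two schedule statements in the randomised-trial paragraph (two sessions in about a week; one to two sessions a week for two weeks). In item 8, say which arm uses which device. If the control game runs on a phone or tablet, the description of it as a VR game in Aim 2 and Phase II must change, since headset exposure would not be matched.

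**Route B, if standard care is what will be delivered.** Define what pupils in that arm receive, amend Aim 2 and Phase II to match, and give controls a date from which the post-gameplay, 3-month and 6-month assessments are timed. Limit the conclusion to Invite Only VR against standard care, without attributing a difference to content alone.

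Under either route, name the comparator in item 13, and state who enters the e-cigarette use data so that Measures and Section IV agree.

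**Cost.** If a control game is already planned, Route A is wording only. Route B needs no added sessions, but it does require rewriting an aim, defining a condition and setting a time anchor. If no control game is planned, Route A means obtaining one and running 2 sessions per control pupil:

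- 115 controls: 115 × 2 = 230 sessions, 115 × 1.5 = 172.5 to 115 × 2 = 230 hours
- 150 controls: 150 × 2 = 300 sessions, 150 × 1.5 = 225 to 150 × 2 = 300 hours

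The headset risks in item 10 and the precautions in item 11 would then apply to controls as well.

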### SECTION III: RECRUITMENT/CONSENT AND ASSENT PROCEDURES

1. **Targeted Enrollment: Give the number of subjects: 300 for sub-study 1; 400 for sub-study #2**

- a. Targeted for enrollment at Yale for this protocol: 300; 400  
b. If this is a multi-site study, give the total number of subjects targeted across all sites: n/a

2. **Indicate recruitment methods below.** Attach copies of any recruitment materials that will be used.

- |                                                          |                                                              |                                             |
|----------------------------------------------------------|--------------------------------------------------------------|---------------------------------------------|
|  Flyers               |  Internet/web postings               |  Radio              |
|  Posters              |  Mass email solicitation             |  Telephone          |
|  Letter                          |  Departmental/Center website         |  Television         |
|  Medical record review*          |  Departmental/Center research boards |  Newspaper          |
|  Departmental/Center newsletters |  Web-based clinical trial registries |  Clinicaltrials.gov |
|  YCCI Recruitment database       |  Social Media (Twitter/Facebook):    |                                             |
|  Other:                          |                                                              |                                             |

\* Requests for medical records should be made through JDAT as described at <http://medicine.yale.edu/ycci/oncore/availableservices/datarequests/datarequests.aspx>

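### The trial's only stated arm sizes (115 + 115 = 230) do not add up to its stated enrolment of 300

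*Combined protocol and SAP*

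**What the plan says.** The paragraph on the randomised trial in Section I, item 4 (Research Plan) begins "We will enroll 300 adolescents to test" the game. Its next sentence randomises participants to "either Invite Only VR (n=115), or receive standard care as usual (n=115"). This is the only place where the protocol gives arm sizes.

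The total of 300 appears in four other statements:

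- Section I, item 1, Specific Aim #2: "Conduct a pilot randomized controlled trial with 300 teens ages 11-15 comparing the Invite Only VR intervention vs. an attention/control non-health-related VR videogame".
- Section I, item 4, Sub-study #1: "In Phase II, we will conduct a randomized controlled trial with 300 teens ages 11-15".
- Section III, item 1 (Targeted Enrollment), twice: "Give the number of subjects: 300 for sub-study 1; 400 for sub-study #2" and "Targeted for enrollment at Yale for this protocol: 300; 400".

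Section I, item 13 (Statistical Considerations) specifies an intention-to-treat sample and says of the mixed model that "participants with missing data need not be excluded as all available data are used in estimating parameters". It gives no expected loss to follow-up, effect size, event rate, power or sample-size calculation.

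**The concern.** Two adjacent sentences give different sizes for the same trial. The plan cannot be followed literally, because 300 enrolled participants do not fit into two arms of 115. With no sample-size calculation, the reader cannot work back to the figure the design needs.

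What is at stake is the planned size: how many adolescents are to be randomised, how many to each arm, and when enrolment is complete. A team could stop at 230 or go on to 300 and point to this paragraph either way. A target that can be read two ways also leaves room to settle the size after the fact.

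**Working it through.** **Inputs**

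- Total enrolment in the randomised trial: 300 (Section I, items 1 and 4).
- Arm sizes at random assignment: 115 and 115 (Section I, item 4).
- Focus-group participants: 4 groups of 5, so 20, aged 12-17 (Section I, items 1 and 4).
- Two-sided significance level: 0.05 (Section I, item 13).

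**Reproducing the stated total**

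- Sum of arms: 115 + 115 = 230. The stated 300 is not reproduced.
- Gap: 300 − 230 = 70, and 70/300 = 23.3%.
- Per arm, assuming equal allocation (implied only by the equal arm sizes): 300/2 = 150, 150 − 115 = 35, and 35/150 = 23.3%.

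**Possible explanations**

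- *A third arm.* Only two conditions are described. A third arm of 115 would give 3 × 115 = 345.
- *Focus-group participants counted in the 300.* 230 + 20 = 250, still 50 short. They belong to Phase I, and items 1 and 4 attach 300 to the randomised trial itself.
- *Loss between enrolment and randomisation.* Item 4 puts eligibility screening before consent. No run-in or later exclusion is described.
- *Attrition allowance.* Inflating 230 by N/(1 − d) gives 230/0.90 = 256 at 10% loss, 230/0.80 = 288 at 20% and 230/0.75 = 307 at 25%. Exactly 300 needs d = 70/300 = 23.3%. The cruder N × (1 + d) gives 230 × 1.30 = 299 at a 30% add-on. Neither rate is in the protocol, and the 115s are attached to assignment, not to completers.

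**Consequence if 230 were the real size**

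- Fraction of the stated total: 230/300 = 76.7%.
- Standard errors relative to 300, other things equal: √(300/230) = √1.3043 = 1.142, about 14% larger.
- Detectable standardised difference at 80% power, two-sided 0.05, (1.960 + 0.842) × √(2/n): 0.369 at n = 115 per arm and 0.323 at n = 150.
- Power for a difference in initiation, over a range of assumed rates:

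| Assumed rates | 115 per arm | 150 per arm |
|---|---|---|
| 10% vs 5% | 0.301 | 0.375 |
| 15% vs 7.5% | 0.436 | 0.538 |
| 20% vs 10% | 0.566 | 0.681 |

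The 80% power level and the initiation rates are my assumptions. The last two calculations also assume equal arms, no clustering and no loss. They show scale only, since the protocol claims no power or precision for them to contradict.

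**The case against.** The arithmetic is not in dispute. The case on the other side is that this is a stale figure with little consequence. The total of 300 is stated five times, including as the formal enrolment target, while 115 is confined to one sentence. Specific Aim #2 calls the trial a pilot, no calculation depends on 115, and no estimate is biased. The protocol also describes no randomisation list, and anyone actually randomised would have an arm, so the fault lies in the planned numbers and not in the allocation process.

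Much of this stands. The weight of the text does favour 300, and the analysis is not invalidated. The same sentence names a control that differs from the other descriptions ("intervention vs. an attention/control non-health-related VR videogame, collecting assessment data at baseline"), which fits the idea of leftover text but does not prove it. That difference is a separate inconsistency, and this point does not depend on it.

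The Section III target is also weaker support than it looks. It covers all of sub-study 1, which includes the 20 focus-group participants. If they are inside the 300, the trial would have 300 − 20 = 280, still 50 more than 230. Items 1 and 4 of Section I carry the point without it.

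What the objection does not do is remove the contradiction. These are the only arm sizes in the plan, they directly follow a total they do not match, and nothing else in the protocol settles which was meant.

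**Conclusion.** The concern holds. The stated arms fall short of the stated enrolment by 70 of 300 (23.3%), or 35 per arm if allocation is equal, and no statement in the protocol accounts for the difference. That much rests only on figures in the text. The 14% increase in standard errors applies only if 230 is the real size. The 76.7% retention (230/300) applies only if 115 was meant as a completer count, which the protocol does not say. The intention-to-treat analysis is unaffected, since its denominator is everyone actually randomised. The point must still be corrected, because the planned size of the trial contradicts itself and cannot be resolved from elsewhere in the document.

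**What to change.** State one number to be randomised and arm sizes that sum to it. The investigator should choose the reading that applies:

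- **300 randomised, equal allocation:** replace 115 with 150 for each arm in the randomised-trial paragraph of Section I, item 4.
- **230 randomised:** change the trial total to 230 in Specific Aim #2 and in both places in Section I, item 4, and align the sub-study 1 target in Section III, item 1.
- **115 per arm is an expected completer count:** label it so, state the implied 23.3% loss with its basis, and give 150 per arm as the number randomised, with all 300 in the intention-to-treat analysis.

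In each case, say in Section III, item 1 whether the 20 focus-group participants are counted in the sub-study 1 target. When the assignment sentence is rewritten, reconcile its control condition with the one in Specific Aim #2 and the Phase II description.

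The cost is wording and corrected figures only.
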